7.3. Vital Signs

Vital signs (systolic and diastolic blood pressure [mmHg], pulse [beats/min]) at each visit and change from baseline at each visit will be summarized for the Safety Analysis Set using descriptive statistics (n, mean, SD, median, Q1, Q3, minimum, and maximum). The baseline value will be defined as the last available value collected on or prior to the date/time of first dose of study drug. Change from baseline to a postbaseline visit will be defined as the postbaseline value minus the baseline value.

In the case of multiple values in an analysis window, data will be selected for analysis as described in Section 3.7.3 (Selection of Data in the Event of Multiple Records in a Window). No inferential statistics will be generated.

A by-subject listing of vital signs (systolic and diastolic blood pressure [mmHg], pulse [beats/min], respiration [breaths/min], and body temperature [$^{\circ}$ C]) will be provided by subject ID number and visit in chronological order.

7.4. Body Weight, Height and BMI

An age- and sex-specific percentile will be derived for each weight, height and BMI measurement according to the downloadable SAS program available on the Centers for Disease Control (CDC) website using the year 2000 growth charts. Methods and SAS program published on the following CDC website will be applied to calculate the percentile {[Centers for Disease Control and Prevention \(CDC\) 2016a](#), [Centers for Disease Control and Prevention \(CDC\) 2016b](#)}.

Body weight, height, BMI and percentiles for body weight, height, BMI at each visit, and change from baseline at each visit will be summarized for the Safety Analysis Set using descriptive statistics (n, mean, SD, median, Q1, Q3, minimum, and maximum).

In the case of multiple values in an analysis window, data will be selected for analysis as described in Section 3.7.3 (Selection of Data in the Event of Multiple Records in a Window). No inferential statistics will be generated.

A by-subject listing of body weight, weight percentile, height, height percentile, BMI and BMI percentile will be provided by subject ID number and visit in chronological order.

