1.5. Rationale for Study Design

This open-label, multi-cohort study is designed to collect safety, efficacy, and PK data to determine the appropriate dose for each age group. The treatment durations of 8 weeks for DAA-naïve subjects without cirrhosis and 12 weeks for DAA-naïve subjects with cirrhosis and DAA-experienced subjects with or without cirrhosis, are based on the Phase 3 POLARIS program. The choice of no comparator or active control group is in line with international guidelines that support single-arm pediatric studies when safety and efficacy have been demonstrated in adults. The minimum number of subjects planned to be enrolled in each age group is considered acceptable to collect PK data to determine the appropriate dose for each age group.

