8.1.3. Secondary Endpoint

The secondary endpoints are:

- Any AE leading to permanent discontinuation of study drug
- The proportion of subjects with sustained virological response (SVR) 12 weeks after cessation of treatment (SVR12) is the key efficacy endpoint
- The proportion of subjects with HCV RNA < LLOQ at 4 or 24 weeks after cessation of treatment (SVR4 and SVR24)
- The proportion of subjects with virologic failure, including on-treatment virologic failure and relapse
- The proportion of subjects with HCV RNA < LLOQ on treatment
- Emergence of viral resistance to SOF, VEL, and VOX during treatment and treatment is discontinued
- HCV RNA change from Day 1
- Growth and development measurements including height and weight percentiles, Tanner Stage, radiographic bone age and two bone turn-over biochemical markers (CTX and P1NP)
- Acceptability, including palatability, and swallowability assessments
- Neuropsychiatric assessments as measured by PedsQL™ Pediatric Quality of Life survey

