1.1. Study Objectives

The primary objectives of this study are as follows:

- To evaluate the steady-state pharmacokinetics (PK) and confirm age-appropriate dose of SOF/VEL/VOX FDC in pediatric subjects with chronic HCV infection

The secondary objectives of this study are as follows:

- To evaluate the safety and tolerability of SOF/VEL/VOX FDC in pediatric subjects with chronic HCV infection
- To evaluate the antiviral efficacy of SOF/VEL/VOX FDC treatment in pediatric subjects with chronic HCV infection, as assessed by the proportion of pediatric subjects with sustained virological response (SVR) 12 weeks after cessation of treatment (SVR12)
- To evaluate the antiviral efficacy SOF/VEL/VOX FDC treatment in pediatric subjects with chronic HCV infection, as assessed by the proportion of pediatric subjects with SVR 4 and 24 weeks after cessation of treatment (SVR4 and SVR24)
- To evaluate the proportion of pediatric subjects with virologic failure, including on-treatment virologic failure and relapse
- To evaluate the kinetics of circulating HCV RNA during treatment and after cessation of treatment
- To evaluate the emergence of viral resistance to SOF, VEL, and VOX during treatment and after cessation of treatment
- To evaluate the effect of SOF/VEL/VOX FDC on growth and development of pediatric subjects during and after treatment
- To evaluate acceptability, including palatability, and swallowability of formulations (as applicable) used in the study
- To assess the effect of treatment with SOF/VEL/VOX FDC on quality of life as measured by PedsQL™ Pediatric Quality of Life survey including neuropsychiatric assessments

CCI

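### SAP 7.4 standardises growth change only on the CDC percentile scale, where an equal SD loss counts for less in children away from the median; z-scores should be added

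*SAP*

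**What the plan says.** Growth is a stated secondary objective: "To evaluate the effect of SOF/VEL/VOX FDC on growth and development of pediatric subjects during and after treatment" (SAP 1.1; Protocol 2 has the same aim). Protocol 8.1.3 lists among the secondary endpoints "Growth and development measurements including height and weight percentiles".

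SAP 7.4 carries this out as follows:

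- **Derivation.** "An age- and sex-specific percentile will be derived for each weight, height and BMI measurement", using the program on the CDC "website using the year 2000 growth charts".
- **Summary.** "Body weight, height, BMI and percentiles for body weight, height, BMI at each visit, and change from baseline at each visit will be summarized", with n, mean, SD, median, quartiles, minimum and maximum.
- **Listing.** "A by-subject listing of body weight, weight percentile, height, height percentile, BMI and BMI percentile will be provided".
- **Inference.** "No inferential statistics will be generated".

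No z-score for height, weight or BMI appears in either document. The only z-scores are for bone mineral density, in the toxicity grading scale (Protocol Appendix 3). There is no control group. Protocol 1.5 says "The choice of no comparator or active control group is in line with international guidelines".

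**The concern.** Of the changes tabulated in SAP 7.4, only the percentile change is adjusted for age and sex. Raw changes in cm and kg include the growth any adolescent would show over 8 weeks of treatment and 24 weeks of follow-up, and without a comparator that growth cannot be subtracted.

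The percentile scale is a poor one for averaging change. It is steep near the median and flat in the tails, so the same loss in SD units moves a child of average height many points and a very short or very tall child few. The shrinkage is stronger below the median, because a loss there moves the child further into the tail. The mean percentile change therefore depends on where the cohort started as well as on how it grew. A reader who takes a small mean change as reassurance could be misled if the children affected were already small.

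**Working it through.** SAP 7.4 states no numerical figure, so there is nothing to reproduce. The trial's power statement concerns PK exposure and has no bearing here. The check is of the scale itself.

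**Inputs.** From the documents: at least 20 adolescents (SAP 1.2, Cohort 1), CDC 2000 percentiles, and mean change from baseline (SAP 7.4). Assumed: starting z-scores z0, losses d in SD units, and percentile = 100 × Φ(z). The documents give no baseline growth distribution, no expected loss and no description of the CDC program's formula.

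**1. One child.** Percentile change = 100 × [Φ(z0 − d) − Φ(z0)].

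| Start z0 | d = 0.1 | d = 0.25 | d = 0.5 |
|---|---|---|---|
| 0 | −4.0 | −9.9 | −19.1 |
| −1 | −2.3 | −5.3 | −9.2 |
| −1.28 (10th percentile) | −1.6 | −3.7 | −6.3 |
| −2 | −0.5 | −1.05 | −1.7 |
| +1 | −2.5 | −6.8 | −15.0 |
| +2 | −0.6 | −1.7 | −4.4 |

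For example, with d = 0.25 a child at the median goes from the 50.0th to the 40.1th percentile, and a child at z = −1 from the 15.9th to the 10.6th. Across these losses the change at the median is 1.7 to 2.1 times that at z = −1, 2.4 to 3.1 times that at the 10th percentile, and about 8 to 12 times that at z = −2. On the z-score scale every row would read −0.1, −0.25 and −0.5.

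**2. How many children this concerns.** If 20 subjects matched the reference population, 20 × Φ(−1) = 3.2 would start below z = −1 and 20 × Φ(−2) = 0.5 below z = −2.

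**3. Cohort mean, uniform loss of 0.25 SD.** With baseline z ~ N(m, s²), mean change = 100 × [Φ((m − 0.25)/√(1 + s²)) − Φ(m/√(1 + s²))].

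| Cohort mean z | s = 0.8 | s = 1.0 | s = 1.2 |
|---|---|---|---|
| 0 | −7.7 | −7.0 | −6.4 |
| −1 | −5.3 | −5.1 | −4.9 |
| −2 | −2.0 | −2.3 | −2.5 |

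The mean z-score change is −0.25 in every cell.

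**4. Who loses matters.** Take ten children at z = 0 and ten at z = −1.5, with a 0.5 SD loss in one half only.

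- Loss in the average half: 0.5 × 100 × [Φ(−0.5) − Φ(0)] = −9.6 points.
- Loss in the short half: 0.5 × 100 × [Φ(−2.0) − Φ(−1.5)] = −2.2 points.

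The mean z-score change is −0.25 both times.

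**5. The sign can change.** Suppose half the children lose 0.5 SD from z = −2 (−1.7 points) and half gain 0.1 SD from z = 0 (+4.0 points). The mean percentile change is +1.2 points, while the mean z-score change is (−0.5 + 0.1)/2 = −0.20.

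**The case against.** The SAP does what the protocol asks: percentiles are the named endpoint, the reference is stated, and nothing is undefined. The by-subject listing shows each child's percentile at every visit, so a reader of about 20 listed subjects could derive z-scores. Other growth outputs are planned: radiographic bone age and the bone markers (SAP 7.6), Tanner stage (7.7) and mid-parental height (7.5). The illustrations rest on assumed losses and statures. The cohort with half its children at z = −1.5 is constructed, since a reference-like group of 20 would have about 20 × Φ(−1.5) = 1.3 at or below that level. Nothing in the documents suggests a short cohort: decompensated liver disease, major illness and malabsorption are excluded, and SAP 3.2 says only subjects without cirrhosis were enrolled.

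Much of this stands. The plan is not in error, the inputs are assumptions, and the more striking cases show what the scale can do, not what is expected. In a cohort of average stature a uniform loss still shows, at about −7 points for 0.25 SD.

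It does not remove the point. Adding z-scores leaves the protocol's percentiles in place. Bone age, bone markers, Tanner stage and a listing of mid-parental height do not give a standardised change in height or weight. A listing lets a reader rebuild a better summary, but it does not correct the tabulated mean.

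**Conclusion.** The concern holds, as a minor point. Percentile change is the only age- and sex-standardised weight, height or BMI change planned for a stated secondary objective in a trial without a comparator, and its mean weights children by baseline stature. A given loss counts about half as much at z = −1 as at the median, and roughly a tenth as much at z = −2. The damping also applies to tall children, though less strongly.

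The size in this trial is unknown, because it depends on a baseline distribution that the documents do not give. If the cohort resembles the reference population, few children lie far from the median and the practical effect is modest. The figures rest on the normal-CDF link between percentile and z-score and on the assumed losses. The analysis is descriptive, so what is affected is how the growth results read; error control is not in question.

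**What to change.** In SAP 7.4, add age- and sex-specific z-scores for height, weight and BMI, giving the value at each visit and the change from baseline with the descriptive statistics already planned. Keep the raw values, percentiles and listings as they are, so the endpoint named in Protocol 8.1.3 is still reported. No confidence interval or test is needed, which keeps to the section's descriptive intent.

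The z-score can be taken as the inverse-normal of the percentile already derived, z = Φ⁻¹(percentile/100), provided unrounded percentiles are used. The cost is one derived variable per measure and some table columns, with no new data, visits or samples.

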7.5. Mid-Parental Height Assessment

The calculation of mid-parental height has been a standard procedure for assessing individual child's future adult height since it was first described by Tanner {Tanner 1970}. Mid-parental height will be calculated as the average of father's and mother's height. For boys, the sex-adjusted mid-parental height will be calculated by adding 2.5 inch or 6.5 cm from the mean of the parents' heights. For girls, will be calculated by subtracting 2.5 inch or 6.5 cm from the mean of the parents' heights. If any one of parents' heights is missing, the calculation will be excluded.

A by-subject listing of parents' heights and derived mid-parental height will be provided by subject ID number in ascending order.

7.6. Bone Age Assessment

Radiographic bone age assessment is performed on Day 1 and End of Treatment.

Radiographic bone age at baseline visit, End of Treatment and change from baseline visit will be summarized for the Safety Analysis Set using descriptive statistics (n, mean, SD, median, Q1, Q3, minimum, and maximum).

Fasting blood samples for bone age biomarkers CTX (C-type collagen sequence) and Procollagen type 1 N-terminal propeptide (P1NP), will be collected at Day 1, Early Termination (if applicable) and posttreatment Week 24.

Each of bone age biomarkers (CTX and P1NP) at baseline visit, Early Termination (if applicable), FU-24 visit and change from baseline visit will be summarized respectively for the Safety Analysis Set using descriptive statistics (n, mean, SD, median, Q1, Q3, minimum, and maximum).

A by-subject listing of radiographic bone age assessment and bone age biomarkers will be provided by subject ID number in ascending order and visit in chronological order.

7.7. Tanner Pubertal Stage Assessment

The Tanner stages will be used to evaluate the onset and progression of pubertal changes. Females will be rated for pubic hair growth and breast development, and males will be rated for pubic hair growth and genitalia development. If the subject is at a Tanner 5 at Day 1, no further Tanner Pubertal Stage Assessments are to be completed. The Tanner stages (Pubic Hair and Breasts for female; Pubic Hair and Genitalia for male) at EOT, FU-12 and FU-24 visit will be summarized by baseline Tanner stages using frequency count and percentage by sex.

Tanner stage results at baseline and during the study will be listed.

7.8. Prior and Concomitant Medications

Medications collected at screening and during the study will be coded using the current version of the World Health Organization (WHO) Drug dictionary. The medications will be categorized as prior or concomitant using the following definitions:

- Prior medications: any medications taken and stopped prior to or on the date of first study drug administration
- Concomitant medications: any medications taken after the date of first study drug administration and up to the last dosing date of study drug

Concomitant medications will be summarized by preferred name using the number and percentage of subjects for the Safety Analysis Set. A subject reporting the same medication more than once will be counted only once when calculating the number and percentage of subjects who received that medication. The summary of concomitant medications will be ordered by preferred term in descending frequency. For drugs with the same frequency, sorting will be done alphabetically.

Summaries will be based on the Safety Analysis Set. No inferential statistics will be generated.

For purposes of analysis, any medication with a stop date that is on or prior to the initial study drug dosing date or a start date that is after the last study drug dosing date will be excluded from a concomitant medication summary. If a partial stop date is entered, any medication with the month and year (if day is missing) or year (if day and month are missing) prior to the initial study drug dosing date will be excluded from the concomitant medication summary. If a partial start date is entered, then any medication with the month and year (if day is missing) or year (if day and month are missing) after the study drug stop date will be excluded from the concomitant medication summary. Medications with completely missing dates will be included in the concomitant medication summary.

A summary of prior medications will not be provided.

All prior and concomitant medications (other than per-protocol study drugs) will be provided in a by-subject listing sorted by subject ID number and administration date in chronological order.

7.9. Neuropsychiatric assessments as measured by PedsQL™ Pediatric Quality of Life survey

The Pediatric Quality of Life (PedsQL™ SF 15) Questionnaires will be completed by all subjects and their parent/legal guardian up to 24-Week Posttreatment visits. The transformed scale scores (0 to 100 scale) at baseline, EOT, or at Early Termination, if applicable, 12-Week Post-Treatment, and 24-Week Post-Treatment visits and change from baseline, change from EOT to posttreatment will be presented for each of the 4 domains of the SF-15 (physical functioning, emotional functioning, social functioning, and school functioning), the psychosocial health summary (emotional, social, and school functioning domains), and the Total Score. Scoring of

the SF15 scales will be performed as described in Scaling and Scoring of the Pediatric Quality of Life Inventory™ (PedsQL™) by James W. Varni. A Wilcoxon signed rank test will be used to explore changes in status from baseline to EOT, or at Early Termination, if applicable, and from EOT to each of the posttreatment time points. Results (p values) will be presented but should be interpreted with caution as multiple endpoints are being tested, and the study has not been powered to test these endpoints. Plot of the mean \pm SD of change from baseline in SF15 summary scores will be presented.

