Subjects unable to swallow the SOF/VEL/VOX FDC (400/100/100 mg) adult tablet (as determined by SOF/VEL/VOX FDC swallowability assessment at Screening or at Day 1) will be re-assigned to a smaller tablet of lower dose or a non-tablet formulation of SOF/VEL/VOX FDC when available. The smaller tablet dose and non-tablet formulation will be included in a protocol amendment, when available.

**Reference Therapy,
Dose, and Mode of
Administration:**

None

Criteria for Evaluation:

Safety: AEs, SAEs, laboratory tests, physical examinations, and vital sign measurements will be collected throughout the study.

Efficacy: Efficacy will be evaluated using scheduled assessments of HCV RNA performed using COBAS[®] AmpliPrep/COBAS[®] TaqMan[®] HCV Test.

Pharmacokinetics: For all subjects, the steady-state PK of SOF, and its major metabolite (GS-331007), VEL and VOX will be assessed. Plasma PK parameters such as C_{max}, C_{tau}, AUC_{tau}, CL_{ss}/F, and Vz/F will be estimated, as appropriate.

Statistical Methods:

The primary endpoint for determining steady-state PK is AUC_{τ} of SOF, GS-331007, VEL and VOX in each cohort. The following plasma PK parameters will be estimated and summarized: AUC_{τ} , C_{\max} , C_{τ} , volume of distribution and clearance, as appropriate. The effect of age and SOF/VEL/VOX FDC dose on PK will be explored.

The main secondary safety endpoint is review of any AEs with a focus on AEs that lead to discontinuation of study drug. In addition, neuropsychiatric examinations as measured by PedsQL™ Pediatric Quality of Life survey, growth and development endpoints (eg, height and weight percentiles, Tanner Pubertal Stage assessment, radiographic bone age assessment and bone age biomarkers) will be assessed.

The key efficacy endpoint is SVR12 in all enrolled and treated subjects.

Other secondary efficacy endpoints include SVR4, SVR24, antiviral activity (on-treatment HCV RNA), on-treatment virologic failure, and relapse.

Acceptability, including palatability, and swallowability assessments are secondary endpoints of the study.

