8.6.4.5. Neuropsychiatric Assessments measured by PedsQL™ Pediatric Quality of Life survey

The data from PedsQL™ Pediatric Quality of Life survey will be summarized by visit and age cohort and treatment duration (8 weeks vs 12 weeks).

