7.11. Changes From Protocol-Specified Safety Analyses

There are no deviations from the protocol-specified safety analyses.

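### PedsQL changes are tested only by exploratory Wilcoxon p-values: no confidence interval is planned, and the net change from baseline to follow-up gets no inference

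*SAP*

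**What the plan says.** Protocol 8.1.3 lists as a secondary endpoint "Neuropsychiatric assessments as measured by PedsQL™ Pediatric Quality of Life survey". Section 2 gives quality of life its own secondary objective. In the synopsis (Statistical Methods) the main secondary safety endpoint is adverse events, and PedsQL is introduced after it: "In addition, neuropsychiatric examinations as measured by PedsQL™ Pediatric Quality of Life survey, growth and development endpoints". The protocol's analysis, in 8.6.4.5, is descriptive: "Pediatric Quality of Life survey will be summarized by visit and age cohort and treatment duration (8 weeks vs 12 weeks".

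SAP 7.9 keeps the descriptive part. It covers scores at each visit, and "change from baseline, change from EOT to posttreatment will be presented for each of the 4 domains of the SF-15", together with the psychosocial summary and the Total Score. It also plans a mean ± SD plot "of change from baseline in SF15 summary scores will be presented".

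SAP 7.9 then adds a test: "A Wilcoxon signed rank test will be used to explore changes in status from baseline to EOT" (or Early Termination), and from EOT to each posttreatment time point. It attaches a warning: "Results (p values) will be presented but should be interpreted with caution as multiple endpoints are being tested". The same sentence says the study has not been powered for these endpoints. No confidence interval, margin or worsening of concern is given, and the default summary for continuous variables in SAP 3 contains no interval.

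SAP 7.11 states: "There are no deviations from the protocol-specified safety analyses".

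**The concern.** The secondary objective asks what treatment does to quality of life. That is an estimation question, and in a single-arm study of about 20 adolescents the useful answer is how large a worsening the data leave open. A signed-rank p-value does not give that, and at this sample size failing to reach significance is common even when scores have truly fallen.

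The choice of contrasts adds to this. The tests cover baseline to EOT and EOT to follow-up, but not baseline to follow-up. A decline that builds in two steps is split between two weak tests. A temporary dip on treatment that fully recovers can appear as a significant posttreatment improvement although the net change is zero.

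The SAP also departs from its own practice. Sections 7.2, 7.3 and 7.4 (laboratory, vital signs, growth) each rule out inferential statistics. SVR12 gets exact 95% CIs without any test (6.1.2), and the PK ratios get 90% CIs (8.1). PedsQL gets p-values and no interval. The protocol plans no PedsQL test, yet the section of the SAP meant for changes from the protocol's safety analyses does not mention it.

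**Working it through.** **Is there a plan figure to reproduce?** Not for PedsQL. The only power statement (protocol 8.9, SAP 1.3) is at least 80% for the AUCtau ratio within 50% to 200%. It concerns PK and gives neither a CV nor an adult sample size.

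**Inputs from the documents.** At least 20 adolescents (SAP 1.2); final analysis in adolescents only (SAP 2.2); within-subject signed-rank test; six scores (four domains, psychosocial summary, Total Score); two respondents; three tested contrasts (baseline to EOT, EOT to FU-12, EOT to FU-24).

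**Assumed, because the documents do not say.** Two-sided 0.05; true worsening of 0.5 SD; normal within-subject changes; n = 20 with data, varied below.

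**1. Miss rate, baseline to EOT.** Exact signed-rank test, changes drawn from N(−0.5, 1), 200,000 simulations at n = 20. The rank sum runs from 0 to 210, and the test rejects at 52 or below, or 158 or above (exact level 0.048). Power is 54.4%, so 45.6% of true worsenings are missed. As a cross-check, the paired t-test has power 56.4%, a miss rate of 43.6%.

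| Setting | Missed |
|---|---|
| n = 15 | 59% |
| n = 18 | 50% |
| n = 20 | 46% |
| n = 25 | 35% |
| n = 20, heavier tails (t, 5 df) | 36.5% |

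About 35 subjects would be needed for 80% power.

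**2. If 0.5 SD means the SD of the score.** The effect in SDs of the change is d = 0.5 / √(2(1 − ρ)), where ρ is the baseline-to-EOT correlation. At n = 20:

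| ρ | d | Missed |
|---|---|---|
| 0.3 | 0.423 | 59% |
| 0.5 | 0.500 | 46% |
| 0.6 | 0.559 | 36% |
| 0.7 | 0.645 | 23.5% |
| 0.8 | 0.791 | 9.5% |

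**3. Choice of contrast.** n = 20, score SD 1, correlation 0.5 between any two visits (so the SD of a change is √(2 × 0.5) = 1), exact test, 100,000 simulations.

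| True pattern | Baseline–EOT | EOT–FU | Either | Baseline–FU (not planned) |
|---|---|---|---|---|
| Down 0.25 at EOT, down 0.5 at FU | 18% | 18% | 34% | 54% |
| Down 0.5 at EOT, full recovery at FU | 54% | 54% | 71% | 5% |

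In the first row the net contrast detects the decline three times as often as either planned test. In the second, EOT to follow-up rejects in the direction of improvement more than half the time although the net change is zero.

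**4. Number of p-values.** If every score and both respondents are tested: 6 × 3 × 2 = 36. With no true change, 36 × 0.05 = 1.8 false positives are expected.

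**5. What an interval would show.** Half-width of the 95% CI for a mean change = t(0.975, 19) / √20 = 2.093 / 4.472 = 0.468 SD of the change. With an observed mean change of zero, the data would still leave open a mean worsening of nearly half an SD.

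**The case against.** The strongest reply is that SAP 7.9 already describes its tests fairly. It uses them to explore, asks for caution, names the multiplicity and admits the lack of power. All of that stands. A reader might infer that the plan treats a p-value above 0.05 as showing no harm. The SAP says nothing of the kind.

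A reader might also infer that PedsQL is reported through p-values alone. It is not: scores, changes and a mean ± SD plot are planned. With n, mean and SD, a reader can work out an interval, including one for the net change. What remains is that the trial's own answer to a stated objective is left to the reader's arithmetic, while a test acknowledged as unpowered is what gets reported formally.

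Nor does neuropsychiatric safety rest on PedsQL alone. Adverse events are the main secondary safety endpoint, and the protocol's grading scale has entries for mood, behaviour and mental status. This limits the weight of the point.

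An interval does not raise power: for a given contrast, a signed-rank CI excludes zero essentially when the test rejects. This is correct. The gain lies in showing the size of worsening still compatible with the data, and in moving the inference to the net contrast. Intervals for six scores, three contrasts and two respondents also number 36, so they need a statement that they are unadjusted.

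Finally, the Wilcoxon test might be called an addition rather than a deviation. But SAP 7.11 is headed as changes from the protocol's safety analyses, and an added test belongs there.

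**Conclusion.** The point holds as a minor improvement to the analysis. The Wilcoxon p-values are the only inference on a named secondary endpoint. They come without an interval, they leave out the net change from baseline to follow-up, and SAP 7.11 does not declare them.

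A non-significant result would say little about worsening: about 46% of true 0.5-SD worsenings would be missed at n = 20. That figure depends on an assumed level, effect size, distribution and sample size. The actual number of adolescents is not given. The range shown is 35% to 59% for n from 25 to 15, 36.5% with heavier tails at n = 20, and 9.5% to 59% if the SD is that of the score. The contrast results rest further on the assumed correlation of 0.5. The absence of an interval, of inference on the net change, and of an entry in 7.11 can be read directly from the documents and depends on none of these assumptions.

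**What to change.** In SAP 7.9:

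- Replace the Wilcoxon p-values with the mean change and its 95% CI, or the Hodges-Lehmann estimate with its signed-rank 95% CI. Do this for baseline to EOT, baseline to FU-12 and baseline to FU-24, for each score and each respondent.
- Keep EOT to posttreatment as a descriptive secondary contrast.
- State that an interval including zero is not evidence of no effect, and that the intervals are not adjusted for multiplicity.

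In SAP 7.11, list this output as an addition to the descriptive summary in protocol 8.6.4.5.

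The cost is SAP wording and changes to existing table shells, with no new data or subjects. The drawback is that the intervals will be wide, about ±0.47 SD of the change at n = 20.
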